11.1.2 Response Criteria for NHL

Definition of Response for NHL Patients: Criteria for response will utilize the IWG Response Criteria for NHL patients⁴².

Complete Response (CR):

Complete disappearance of all detectable clinical evidence of disease and disease related symptoms if present before therapy.

- In patients with no pre-treatment PET scan, or if the PET scan was positive before therapy, a post-treatment residual mass of any size is permitted as long as it is PET-negative.
- The spleen and/or liver, if considered enlarged prior to therapy on the basis of a physical examination or CT scan, should not be palpable on physical examination and should be considered normal size by imaging studies, and nodules related to lymphoma should disappear. However, determination of splenic involvement is not always reliable because a spleen considered normal in size may still contain lymphoma, whereas an enlarged spleen may reflect variations in anatomy, blood volume, the use of hematopoietic growth factors, or causes other than lymphoma.
- If the bone marrow was involved by lymphoma before treatment, the infiltrate must have cleared on repeat bone marrow biopsy. The biopsy sample on which this determination is made must be adequate (with a goal of > 20 mm unilateral core). If the sample is indeterminate by morphology, it should be negative by immunohistochemistry. A sample that is negative by immunohistochemistry, but that demonstrates a small population of clonal lymphocytes by flow cytometry, will be considered a CR until data become available demonstrating a clear difference in patient outcome.

Partial Response (PR):

- At least a 50% decrease in the sum of the product of the diameters (SPD) of up to six of the largest dominant nodes or nodal masses. These nodes or masses should be selected prior to initiation of therapy according to all of the following: a) they should be clearly measurable in at least two perpendicular dimensions; b) if possible, they should be from disparate regions of the body; and c) they should include mediastinal and retroperitoneal areas of disease whenever these sites are involved.
- No increase should be observed in the size of other nodes, liver, or spleen.
- Splenic and hepatic nodules must regress by $\leq 50\%$ in their SPD, or, for single nodules, in the greatest transverse diameter.
- With the exception of splenic and hepatic nodules, involvement of other organs is usually assessable and no measurable disease should be present.
- Bone marrow assessment is irrelevant for determination of a PR if the sample was positive before treatment. However, if positive, the cell type should be specified (e.g., large-cell lymphoma or small neoplastic B cells). Patients who achieve a CR by the above criteria, but who have persistent morphologic bone marrow involvement, will be considered partial responders. When the bone marrow was involved before therapy and a clinical CR was achieved, but with no bone marrow assessment after treatment, patients should be considered partial responders.
- No new sites of disease should be observed.
- If performed, the post-treatment PET should be positive in at least one previously involved site.

Stable Disease (SD):

Patient fails to attain the criteria needed for a CR or PR, but does not fulfill those for progressive disease (see below). If performed, the PET should be positive at prior sites of disease, with no new areas of involvement on the post-treatment CT or PET.

Progression (PD) or Relapse:

- Lymph nodes should be considered abnormal if the long axis is > 1.5 cm, regardless of the short axis. If a lymph node has a long axis of 1.1 to 1.5 cm, it should only be considered abnormal if its short axis is > 1.0 . Lymph nodes ≤ 1.0 by ≤ 1.0 will not be considered as abnormal for relapse or progressive disease.
- Appearance of any new lesion > 1.5 cm in any axis during or at the end of therapy, even if other lesions are decreasing in size. Increased FDG uptake in a previously unaffected site should only be considered relapsed or progressive disease after confirmation with other modalities. In patients with no prior history of pulmonary lymphoma, new lung nodules identified by CT are mostly benign. Thus, a therapeutic decision should not be made solely on the basis of the PET without histologic confirmation.
- At least a 50% increase from nadir in the SPD of any previously involved nodes, or in a single involved node, or the size of other lesions (e.g., splenic or hepatic nodules). To be considered progressive disease, a lymph node with a diameter of the short axis of $<$

1.0 cm must increase by $\geq 50\%$ and to a size of 1.5 x 1.5 cm, or > 1.5 cm in the long axis.

- At least a 50% increase in the longest diameter of any single previously identified node > 1.0 cm in its short axis.

Lesions should be PET-positive if a typical FDG-avid lymphoma or the lesion was PET- positive prior to therapy unless the lesion is too small to be detected with current PET systems (< 1.5 cm in its long axis by CT).

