13.5 Definition of Secondary Endpoints

13.5.1 Toxicity will be graded by CTCAEv4.0. A copy of the CTCAE version 4.0 can be downloaded from the CTEP web site
http://ctep.cancer.gov/protocolDevelopment/electronic_applications/ctc.htm.

13.5.2 Clinical response and survival will be measured by:

- International Working Group Criteria for NHL patients.
- IWCLL 2008 Guidelines for CLL patients.

Response criteria are detailed in Section 10.

Responders will be defined as those with complete response (CR) or partial response (PR). Overall response rate (ORR) will be calculated as the number of evaluable responders divided by the total number of evaluable patients and will be analyzed by cohort. All patients who receive at least one dose of study medication will be included in the ORR and progression free survival.

Progression Free Survival (PFS): PFS will be calculated from the date of study enrollment to disease progression or death, whichever occurs first. Patients who do not progress or die will be censored at the time of last contact with response assessment by physical exam and laboratory studies.

Overall Survival (OS): OS will be calculated from the date of study enrollment to death. Patients who do not die will be censored at the time of last contact. This will be analyzed in each cohort independently.

13.5.3 Response as related to chronic lymphocytic leukemia (CLL) karyotype and IgVH mutational status. Response criteria are detailed in Section 10.

13.5.4 For Cohort 3, the rate of deepening of response is defined as the percentage of patients who attain a MRD negative complete response (MRD- CR) at the end of 14 cycles of selinexor plus ibrutinib.

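### The NHL partial-response criterion for splenic and hepatic nodules is printed as a ceiling on shrinkage (≤50%) where the protocol's other response rules imply a floor (≥50%)

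*Combined protocol and SAP*

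**What the plan says.** Section 11.1.2 lists the NHL response criteria. For PR, the organ-nodule item reads: "Splenic and hepatic nodules must regress by $\leq 50\%$ in their SPD, or, for single nodules, in the greatest transverse diameter". The first item in the same list, for nodes, reads: "At least a 50% decrease in the sum of the product of the diameters (SPD) of up to six of the largest dominant nodes".

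Other rules that bear on the same lesions or the same category:

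- CR (11.1.2): where the spleen or liver was enlarged before therapy, "nodules related to lymphoma should disappear".
- PR, marrow item (11.1.2): "Patients who achieve a CR by the above criteria, but who have persistent morphologic bone marrow involvement, will be considered partial responders". The same holds if the marrow was involved before therapy and was not re-examined.
- SD (11.1.2): "Patient fails to attain the criteria needed for a CR or PR, but does not fulfill those for progressive disease (see below").
- CLL PR (11.1.3): enlargement of the spleen or liver must fall by half or more.

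Section 11.1.1 says that evaluable patients are classified by the definitions that follow it. Section 13.5.2 then uses the result: "Responders will be defined as those with complete response (CR) or partial response (PR"). Section 13.8.2 reports ORR at the MTD with an exact 95% interval and summarises degree of response by disease group and dose level. Section 11.1.4 starts the duration of response when CR or PR is first met.

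**The concern.** A partial response is a minimum amount of improvement, so each size criterion should set a floor on shrinkage. The nodule item sets an upper limit instead. A patient whose nodules shrink well fails it, and a patient whose nodules barely change meets it.

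The resulting error has no fixed direction. Some patients with good organ response would drop from PR to SD, and some with almost unchanged organ disease would be counted as responders. The net bias in ORR therefore cannot be signed in advance or described as conservative. In a multi-center study, some assessors may apply the printed item and others the cited published criteria, so the same findings could be coded differently at different sites.

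**Working it through.** The plan states no figure that depends on this item, so there is nothing to reproduce. The check has three steps.

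**1. Truth table.** Let r be the percentage regression of the nodules (SPD or, for a single nodule, greatest transverse diameter). The printed rule requires some regression and r ≤ 50. The opposite direction requires r ≥ 50.

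| r (%) | Printed rule (≤50) | Opposite rule (≥50) |
|---|---|---|
| 0 | not met | not met |
| 5 | met | not met |
| 49 | met | not met |
| 50 | met | met |
| 51 | not met | met |
| 80 | not met | met |
| 100 | not met | met |

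Among patients whose nodules regress at all, the two rules agree only at exactly 50%.

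**2. Comparison with the neighbouring rules.**

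- *Nodal PR item.* It requires a decrease of at least 50%, which is a floor. The two items cover different lesions, so a patient can satisfy both. The conflict here is of direction within one category.
- *CR and marrow items together.* A patient with nodules who meets CR has r = 100. If marrow involvement persists, the marrow item makes that patient a partial responder. The nodule item excludes r = 100 from PR. The two items give opposite answers for the same patient, so the PR list contradicts itself.
- *CLL PR item.* The corresponding spleen and liver rule in 11.1.3 is a floor of 50%.

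Now take an NHL patient with nodes down 60%, every other PR item met, and residual disease:

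- Nodules down 80%: the nodule item fails, so not PR. Residual disease means not CR. There is no progression, so not PD. The SD definition then applies.
- Nodules down 5%: the nodule item is met, so PR.

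**3. Size of one reclassification.** Inputs: as many as 10 NHL and 10 CLL patients accrued at the MTD (13.1), and an exact interval for ORR (13.8.2).

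The shift in ORR from one patient is 1/n:

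- n = 10: 1/10 = 10 percentage points.
- n = 20 (both diseases pooled): 1/20 = 5 percentage points.

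The exact (Clopper–Pearson) 95% limits for x of n are the 0.025 quantile of Beta(x, n − x + 1) and the 0.975 quantile of Beta(x + 1, n − x). For n = 10:

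- x = 3: Beta(3, 8) and Beta(4, 7) give 6.7% to 65.2%.
- x = 4: Beta(4, 7) and Beta(5, 6) give 12.2% to 73.8%.

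**The case against.** **The published criteria are named.** Sections 11.1, 11.1.2 and 13.5.2 all say that the IWG criteria are used, so an assessor may apply those and never act on the printed item. This is a real mitigation, and it means that literal misclassification is not certain. It does not remove the problem: 11.1.1 directs classification by the definitions written in the protocol, and those definitions are what a monitor would check against.

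**The symbol may be a conversion artefact.** The point rests on one character, and conversion from PDF can corrupt symbols. That cannot be fully excluded. It is unlikely, because ≥ appears correctly in the nearby progression criteria of 11.1.2. Checking the source file settles it.

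**The authors may have meant regression to at most 50% of baseline.** That leaves 100 − r ≤ 50, which is r ≥ 50. It is the same corrected rule, so this reading confirms that the printed wording is wrong.

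**The reach is small.** This stands. A reader might infer that every NHL patient with liver or spleen nodules is misclassified, or that trivial nodule shrinkage alone earns a PR. The documents support neither. The nodule item is one of several, and the other PR items must still be met. Patients in CR or PD, or with less than a 50% nodal decrease, are classified the same whichever way the symbol points. The number affected could be zero.

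**No decision depends on it.** This also stands. A reader might infer that the error threatens the trial's main conclusions. The primary endpoint is DLT (13.4), and dose-finding and MTD selection use DLT only (13.7). The Cohort 3 rule counts MRD-negative CRs in CLL/SLL (13.2). PFS depends on progression or death, and NHL treatment may continue until progression (5.19), so PR versus SD changes neither. NHL ORR has no decision threshold, and the two illustrative intervals overlap over most of their length.

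**Conclusion.** The criterion is wrong as printed, and this follows from the protocol's own rules without recourse to the cited source. The strongest evidence is the conflict inside the PR list: complete disappearance of nodules with residual marrow disease is PR by one item and excluded from PR by another.

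The effect is confined to NHL patients with splenic or hepatic nodules who otherwise meet PR, and to the secondary ORR, the degree-of-response summaries and duration of response. Each affected patient moves ORR by 10 points if the denominator is 10 and by 5 points if it is 20. Those denominators are assumptions: the expansion sizes are maxima, patients treated at the MTD during dose-finding may be added, and 13.5.2 (by cohort) and 13.8.2 (patients at the MTD) do not fix one denominator for ORR. The total effect cannot be stated because the number of patients with such nodules is not given.

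This should be fixed, as a correction to a secondary endpoint definition. It is not a flaw in the primary design.

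**What to change.** 1. Confirm the symbol in the protocol source file.
2. If it is printed as ≤50%, change it to ≥50% in the nodule item of the NHL PR criteria in 11.1.2, so that nodules must regress by at least half in SPD or, for a single nodule, in greatest transverse diameter.
3. Re-check every NHL response already coded in a patient with liver or spleen nodules, and correct PR and SD codes, and response start dates, where the direction of the rule changed the result.

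The cost is one symbol in an amendment and a review of the response forms for that subset. No visit, scan or patient procedure is added.

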11.1.3 Response Criteria for CLL Patients

Definition of Response for CLL Patients: Criteria for response will utilize the IWCLL Response criteria¹⁴.

Complete response (CR):

CR requires all of the following criteria as assessed at least 2 months after completion of therapy:

- Peripheral blood lymphocytes (evaluated by blood and differential count) below $4 \times 10^9/L$ ($4000/\mu L$). The presence of minimal residual disease (MRD) after therapy should be assessed. The sensitivity of the method used to evaluate for MRD should be reported.
- Absence of significant lymphadenopathy (e.g., lymph nodes > 1.5 cm in diameter) by CT scan of the abdomen, pelvis, and thorax.
- No hepatomegaly or splenomegaly by physical examination.
- Absence of constitutional symptoms.
- Blood counts above the following values:
 - Neutrophils more than $1.5 \times 10^9/L$ ($1500/\mu L$) without need for exogenous growth factors.
 - Platelets more than $100 \times 10^9/L$ ($100\,000/\mu L$).
 - Hemoglobin more than 110 g/L (11.0 g/dL) without red blood cell transfusion or need for exogenous erythropoietin.
- A marrow aspirate and biopsy should be performed at least 2 months after the last treatment and if clinical and laboratory results as above demonstrate that a CR has been achieved.
 - To define a CR, the marrow sample must normocellular for age, with less than 30% of nucleated cells being lymphocytes. Lymphoid nodules should be absent. If lymphoid nodules are present then these nodules should be recorded as nodular PR. However, immunohistochemistry should be performed to define whether these nodules are composed primarily of T cells or lymphocytes other than CLL cells or of CLL cells. If the marrow is hypocellular, a repeat determination should be performed after 4 weeks, or until peripheral blood counts have recovered. However, this time interval should not exceed 6 months after the last treatment. A marrow biopsy should be compared with that of pretreatment marrow. The quality of the CR should be assessed for MRD by flow cytometry or by immunohistochemistry (IHC).

CR with incomplete marrow recovery (CRi):

All the criteria for a CR (including the marrow examination) have been met though there is persistent anemia or thrombocytopenia or neutropenia apparently unrelated to CLL but related to drug toxicity.

Partial response (PR) PR is defined as follows:

- A decrease in the number of blood lymphocytes by 50% or more from the value before therapy.
- Reduction in lymph node size by 50% or more either in the sum products of up to 6 lymph nodes, or in the largest diameter of the enlarged lymph node(s) detected prior to therapy.
- No increase in any lymph node, and no new enlarged lymph node. In small lymph nodes (< 2 cm), an increase of less than 25% is not considered to be significant.
- A reduction in the noted pretreatment enlargement of the spleen or liver by 50% or more, as detected by CT scan.
- The blood count should show one of the following results:
- Neutrophils more than $1.5 \times 10^9/L$ ($1500/\mu L$) without need for exogenous growth factors.
- Platelet counts greater than $100 \times 10^9/L$ ($100\,000/\mu L$) or 50% improvement over baseline.
- Hemoglobin greater than 110 g/L (11.0 g/dL) or 50% improvement over baseline without requiring red blood cell transfusions or exogenous erythropoietin.

Progressive Disease:

Characterized by at least one of the following:

- Appearance of any new lesion, such as enlarged lymph nodes (>1.5 cm), splenomegaly, hepatomegaly, or other organ infiltrates.
- An increase by 50% or more in greatest determined diameter of any previous site.
- An increase in the previously noted enlargement of the liver or spleen by 50% or more or the de novo appearance of hepatomegaly or splenomegaly.
- An increase in the number of blood lymphocytes by 50% or more with at least 5000 B-lymphocytes per microliter.
- Transformation to a more aggressive histology (e.g., Richter syndrome). Whenever possible, this diagnosis should be established by lymph node biopsy.
- Occurrence of cytopenia (neutropenia, anemia, or thrombocytopenia) attributable to CLL. During therapy, cytopenias cannot be used to define disease progression.
- The progression of any cytopenia (unrelated to autoimmune cytopenia), as documented by a decrease of Hb levels by more than 20 g/L (2 g/dL) or to less than 100 g/L (10 g/dL), or by a decrease of platelet counts by more than 50% or to less than $100 \times 10^9/L$ ($100\,000/\mu L$), which occurs at least 3 months after treatment, defines disease progression, if the marrow biopsy demonstrates an infiltrate of clonal CLL cells.

Stable Disease:

Patients who do not fulfill the criteria for complete or partial response as defined above but do not exhibit progressive disease will be considered as having stable disease.

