Due to this research and other strong preclinical data, ibrutinib entered clinical trials in patients with relapsed and refractory CLL. Sixteen of the 56 patients with B-cell malignancies in an early phase I trial of ibrutinib¹³ were patients with CLL. Eleven of these 16 patients experienced rapid reduction of lymphadenopathy during cycle one of treatment, which was accompanied by an increase in peripheral lymphocytosis suggesting a redistribution of CLL cells from the lymph nodes into the peripheral blood. Ibrutinib was generally well-tolerated and of all toxicities, the most common adverse events were typically grade 1 or 2, including diarrhea (42.9%), nausea (41.1%), fatigue (37.5%), myalgia (37.5%), and dyspepsia (30.4%)¹³. This trial led to a landmark phase Ib/II study in 85 relapsed and refractory CLL patients⁸ where patients were assigned to receive either 420mg (n=51) or 840mg (n=34) of oral ibrutinib daily until disease progression or intolerable adverse events. The overall response rate (ORR) was 71% in both dose cohorts when based on standard response criteria¹⁴. An additional 20% and 15% of patients in the 420mg and 840mg cohorts, respectively, achieved a partial response with residual lymphocytosis⁸. Prolonged lymphocytosis during ibrutinib therapy has subsequently been found not to indicate a suboptimal response to therapy¹⁵. Response rates were not different between several known high-risk populations, with the exception of a worse response seen in patients with mutated-IgVH. Correlative analyses demonstrated a greater than 90% occupancy of the pharmacodynamics BTK probe and similar response rates between the groups that received 420 mg and 840 mg, which provided support for the use of the 420 mg dose in CLL patients. Again, ibrutinib was well-tolerated and the most common adverse events were grade 1 or 2 and included diarrhea (47%), and upper respiratory tract infection (33%), fatigue (28%), and most adverse events resolved without holding therapy. The 26-month estimated rates of progression-free survival (PFS) and overall survival (OS) were 75% and 83%, respectively. This study led to the ultimate approval of ibrutinib for relapsed/refractory CLL patients by the US Food and Drug Administration (FDA). Although these results are very promising, there remains a subset of high risk, most notably patients with del(17p13.1) karyotype, who demonstrated a shorter PFS and OS of 57% and 70%, respectively⁸.

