5.19 Duration of Therapy

In the absence of treatment delays due to adverse event(s), treatment may continue indefinitely or until one of the following criteria applies:

- Disease progression,
- Intercurrent illness that prevents further administration of treatment,
- Unacceptable adverse event(s),
- Patient decides to withdraw from the study, or
- General or specific changes in the patient's condition render the patient unacceptable for further treatment in the judgment of the investigator.
- Patients enrolled in Cohort 3 will discontinue therapy in a response-adapted manner. All patients will discontinue selinexor after 14 cycles. Patients who achieve a MRD negative CR at 14 cycles will discontinue both selinexor and ibrutinib. Patients who achieve a MRD – PR will discontinue both selinexor and ibrutinib at discretion of treating physician. Patients with any other response are recommended to continue ibrutinib indefinitely.

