6. DOSING DELAYS/DOSE MODIFICATIONS

Toxicities that occur in cycle 1 that are DLTs (Section 4.2) will result in protocol removal. Adverse events that are not defined as DLTs and / or occur in cycles 2 and higher will lead to dose delays and modifications as detailed below. No dose reduction below ibrutinib 140 mg and selinexor 20 mg/week will be allowed. If a patient experiences several adverse events, and there are conflicting recommendations, the investigator should use the recommended dose adjustment that reduces the dose to the lowest level. Missed doses will not be replaced. Treatment delays for adverse events exceeding 28 days will lead to protocol removal unless approved by the principal investigator.

Ibrutinib-related lymphocytosis, for the purposes of this protocol, is defined as an elevation in blood lymphocyte count of $\geq 50\%$ compared with baseline count in conjunction with unequivocal improvement in at least 1 other disease-related parameter including lymph node size, spleen size,

hematologic parameters (hemoglobin or platelets), or disease-related symptoms. Ibrutinib-associated treatment-related lymphocytosis generally occurs within the first few weeks of therapy, peaks within the first few months, and resolves slowly. Patients with isolated lymphocytosis in the setting of reduced disease burden or improvement in hemoglobin/platelets should not be considered to have progressive disease.

Asymptomatic treatment-related lymphocytosis should not be considered an adverse event. Subjects with treatment-related lymphocytosis in the absence of other disease-related symptoms should be encouraged to remain on study treatment and continue with all study-related procedures.

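### Section 11.1.3 ties CLL complete response to a two-month gap after therapy, in conflict with on-treatment assessment and with the Cohort 3 endpoint at 14 cycles

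*Combined protocol and SAP*

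**What the plan says.** **Timing of CR in CLL.** Section 11.1.3 opens its CR definition with "CR requires all of the following criteria as assessed at least 2 months after completion of therapy" and adds "A marrow aspirate and biopsy should be performed at least 2 months after the last treatment". CRi requires every CR criterion, the marrow included, so it carries the same timing. Section 11 gives no on-treatment variant.

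**When response is assessed.** Section 11.1 schedules assessments after 1 and 3 months of therapy, then every 3 months to one year, then every 6 months until progression, with no cap on treatment length. The study summary before the table of contents plans marrow biopsies to confirm CR, and yearly thereafter, while treatment may continue.

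**Cohort 3.** Sections 13.2 and 13.5.4 define success as MRD-negative CR once 14 cycles of the combination have been given; 3 or more of 10 makes the regimen promising. Section 5.19 says "Patients who achieve a MRD negative CR at 14 cycles will discontinue both selinexor and ibrutinib". The Cohort 3 calendar puts a marrow at Cycle 14 Day 1 and the first off-therapy reassessment at 4 to 6 weeks.

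**Lymphocytosis.** PR in Section 11.1.3 lists "A decrease in the number of blood lymphocytes by 50% or more from the value before therapy", and there is no category for PR with lymphocytosis. PD lists "An increase in the number of blood lymphocytes by 50% or more with at least 5000 B-lymphocytes per microliter", without exception. Section 6, on dosing, says "Patients with isolated lymphocytosis in the setting of reduced disease burden or improvement in hemoglobin/platelets should not be considered to have progressive disease". Section 2.3 reports an ORR of 71% by standard criteria in the cited ibrutinib study, and then: "An additional 20% and 15% of patients in the 420mg and 840mg cohorts, respectively, achieved a partial response with residual lymphocytosis".

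**NHL nodules.** Section 11.1.2 reads "Splenic and hepatic nodules must regress by $\leq 50\%$ in their SPD", whereas nodes in the same list must shrink by 50% or more.

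**The concern.** The CLL criteria are worded for a finite course of treatment followed by a rest. This trial gives continuous therapy and assesses response while it is being given. The CR definition and the schedule therefore do not fit together.

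In Cohort 3 the mismatch is circular. Section 5.19 makes stopping both drugs follow from an MRD-negative CR, but Section 11.1.3 does not let that CR be declared until treatment has been over for two months. MRD-negative CR is the cohort's only go/no-go criterion, so its result would depend on whether the reader applies the definition or sets it aside.

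Lymphocytosis raises two smaller matters. The exception that keeps isolated lymphocytosis from being called PD sits in the dosing section, and Section 11.1.3 does not point to it, although PFS and duration of response are built on PD. Nor does the plan say how a patient with shrinking nodes and persistent lymphocytosis will appear in the response tables.

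**Working it through.** **1. The plan's own table.** Inputs from Section 13.2: n = 10, success at 3 or more, exact binomial upper tail. At a true rate of 0.30:

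P(X ≥ 3) = 1 − [0.7^10 + 10(0.3)(0.7^9) + 45(0.3^2)(0.7^8)] = 1 − [0.0282 + 0.1211 + 0.2335] = 0.617.

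| True rate | Printed | Recomputed |
|---|---|---|
| 0.10 | 0.070 | 0.0702 |
| 0.20 | 0.322 | 0.3222 |
| 0.25 | 0.474 | 0.4744 |
| 0.30 | 0.617 | 0.6172 |
| 0.35 | 0.738 | 0.7384 |
| 0.40 | 0.833 | 0.8327 |

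All six values agree. The table assumes that every true conversion can be classified as MRD-negative CR at the stated time.

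**2. Section 11.1.3 applied literally.** A patient treated through cycle 14 is not two months past therapy when cycle 14 ends. The classifiable rate is then 0, and P(X ≥ 3) = 0 at every true rate. The marrow at Cycle 14 Day 1 falls during treatment. The first off-therapy visit, at 4 to 6 weeks, is also too early, since two months is about 61/7 = 8.7 weeks. Patients with responses other than MRD-negative CR or PR are recommended to stay on ibrutinib, so for them the window need not open.

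**3. In between: late confirmation accepted.** Assume that only a fraction f of true converters can be confirmed two months or more after both drugs stop. The documents give no value for f. With a true rate of 0.30, the effective rate is 0.30 × f:

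| f | Effective rate | P(X ≥ 3 of 10) |
|---|---|---|
| 0.25 | 0.075 | 0.034 |
| 0.50 | 0.150 | 0.180 |
| 0.75 | 0.225 | 0.398 |
| 1.00 | 0.300 | 0.617 |

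**4. PR with lymphocytosis.** From Section 2.3, the 420 mg group gives 71% without this category and 71% + 20% = 91% with it; the 840 mg group gives 71% + 15% = 86%. If those shares carried over to 10 expansion CLL patients, about 10 × 0.20 = 2 (or 1.5 at 15%) would fall in it. The chance of at least one is 1 − 0.80^10 = 0.89 (or 1 − 0.85^10 = 0.80). For illustration, the exact 95% interval is 0.35 to 0.93 for 7/10 and 0.55 to 1.00 for 9/10. Section 6 says the lymphocytosis starts within weeks, peaks within months and clears slowly, so the 1- and 3-month assessments can fall inside it.

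**5. PD.** Sections 6 and 11.1.3, set side by side, give different answers for a patient whose lymphocytes rise by half or more, to the stated B-cell count, while nodes shrink: not PD under the first, PD under the second.

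**The case against.** **Intent is clear.** The trial-specific passages all point to an on-treatment call: the summary's marrow confirmation during continuing therapy, Section 5.19 acting on the response at 14 cycles, the Cycle 14 Day 1 marrow, and the assessment schedule in Section 11.1. On this view the two-month wording is generic text carried over, and no site would apply it. That stands as a reading of intent. A reader might infer from Section 11.1.3 that Cohort 3 is bound to fail; the documents do not support that. But intent does not amend the operative definition. Section 13.5.2 sends the reader to the response criteria, and those say something else.

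**Lymphocytosis is not simply PD.** A reader of Section 11.1.3 alone might infer that a nodal responder with lymphocytosis scores as progressed. Section 6 excludes that when disease burden falls or hemoglobin or platelets improve. What remains is a missing link between the two sections.

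**Leaving out PR with lymphocytosis is a legitimate choice.** No passage counts it as a response, and the PR rule matches the standard criteria behind the cited 71%. One might infer a contradiction over ORR, but there is none. ORR here is descriptive, with an exact interval and no threshold, and the 71% and 91% come from monotherapy. Cohort 3 is little affected, since its patients enter in PR after at least 12 cycles. The point therefore concerns reporting, mainly in Cohorts 1 and 2.

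**The NHL sign may be a typing or text-extraction error.** That is quite possible, and it is secondary.

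**Conclusion.** The conflict is real and lies in the endpoint definition. As written, Section 11.1.3 bars CR and CRi for any CLL patient still on treatment and cannot be reconciled with an MRD-negative CR scored when 14 cycles end. Under the literal reading, the chance of meeting the Cohort 3 rule is 0 instead of the printed 0.070 to 0.833; under the evidently intended reading, the table is correct as printed. The intermediate values depend on an assumed f and show only how far the result could move if confirmation were left to follow-up after stopping. The documents support a conflict between passages, not an impossible endpoint.

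The lymphocytosis exception needs to be stated once, where PD is defined. The 20 percentage points between 71% and 91% describe the cited monotherapy data, not a forecast for this combination. The nodule sign needs only a check.

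**What to change.** - **CR timing.** In Section 11.1.3, state that for this protocol's endpoints CLL CR and CRi, and the Cohort 3 MRD-negative CR, are assessed on treatment at the scheduled time points. For Cohort 3, name the cycle 14 assessment and its marrow, and align the calendar's Day 1 marrow with the end-of-14-cycles wording in 13.2 and 13.5.4. Do not add a confirmation step at the next visit: by then selinexor has stopped, under Section 5.19 both drugs have stopped in MRD-negative CR, and no later routine marrow is marked. Section 5.19 must be reconciled with this definition; the stopping rule itself is for the investigators.
- **PD in CLL.** Carry the Section 6 exception into the PD criteria so that PFS and duration of response follow one rule.
- **ORR in CLL.** Report PR with lymphocytosis as a separate category and give ORR with and without it.
- **NHL nodules.** Check the inequality sign in Section 11.1.2 against the source and reconcile it with the rule for nodes.

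The cost is wording in Section 11.1 and an extra line in the response table. Sample size, the 3-of-10 rule and the probabilities in Section 13.2 are unchanged. The price is comparability: an on-treatment CR is not directly comparable with a post-therapy CR in other studies, and reports should say so.
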